**Table 1. Schedule for outcome and mediator measures**

| Measure                   | Pregnancy             | Postpartum (W-week, M-month) |    |    |    |    |    |    |                |                |
|---------------------------|-----------------------|------------------------------|----|----|----|----|----|----|----------------|----------------|
|                           | Enrollment (pre-test) | W1                           | W2 | M1 | M2 | M3 | M4 | M5 | M6 (post-test) | M9 (follow-up) |
| Outcomes           |                       |                              |    |    |    |    |    |    |                |                |
| Smoking status            | X                     | X                            | X  | X  | X  | X  | X  | X  | X              | X              |
| Breastfeeding (BF) status | BF intention          | X                            | X  | X  | X  | X  | X  | X  | X              | X              |
| Mediators          |                       |                              |    |    |    |    |    |    |                |                |
| Oxytocin and prolactin    |                       |                              |    | X  |    | X  |    | X  |                |                |
| Mother-infant bonding     |                       | X                            | X  | X  | X  | X  | X  | X  | X              | X              |
| Mother-infant interaction |                       |                              |    | X  |    | X  |    | X  |                |                |
| Maternal stress           | X                     | X                            | X  | X  | X  | X  | X  | X  | X              | X              |
| Maternal negative affect  | X                     | X                            | X  | X  | X  | X  | X  | X  | X              | X              |

**Timing of maternal postpartum smoking relapse.** The participant will use a calendar to record the daily number of cigarettes smoked, if any, throughout the study period. Based on SRNT guidelines, the date of postpartum relapse will be defined as the first day after delivery on which an ex-smoker has smoked for 7 consecutive days, or has smoked at least once each week over 2 consecutive weeks. Similar definitions were used in previous studies on postpartum smoking relapse. The self-reported smoking abstinence will be biochemically confirmed by urine cotinine tests with HPLC-MS/MS assay performed by an outside laboratory (Kaleida Health Lab, Buffalo, NY). As recommended by SRNT, a cut-off point of 50 ng/mL urine cotinine will be used to define current smoking. There is a possibility that some participants may relapse during pregnancy (*prenatal* smoking relapse). If the relapse happens before randomization, they will be removed from this study. Otherwise, they will continue to receive breastfeeding intervention and be included in intent-to-treat analysis.

**Breastfeeding duration.** We will measure the initiation, duration, and exclusivity of breastfeeding by interviewing the mother at each postpartum visit using a questionnaire modified from 2 US national birth cohorts. Postpartum mothers will report their current feeding method, frequency, and duration of breastfeeding and/or formula use. Breastfeeding status will be visually verified by a female research staff,

looking for one of the following indicators of successful breastfeeding in the infant – audible swallowing, a regular suck/swallow/breath pattern, or visible milk in the infant's mouth after they are not latched anymore. For a mother who pumps milk, staff will observe pumping combined with the resulting milk being fed to the infant. This visual verification of breastfeeding/pumping was acceptable to participants in [name] study.

**3.1.9 Mediator measures.** *Maternal plasma oxytocin and prolactin.* The release of oxytocin and prolactin is often pulsatile and stimulated by suckling or pumping, and also varies across postpartum periods. To capture hormonal changes, we will measure the baseline and peak levels of these two hormones during a typical feeding session (\$40 extra compensation/session) in 1, 3, and 5 months postpartum (**Table 1**). The hormonal response to feeding will be calculated as the difference between the baseline and the peak during feeding. Based on a published protocol (co-authored by [name], Consultant), the mother will bring her infant to the PI's lab at 1PM for an observed feeding session in a quiet dedicated room administrated by the PI and a phlebotomist. A 20 gauge Venflon cannula will be inserted into the mother's forearm vein to enable multiple blood draws. To reduce the impact of experimental manipulation (e.g., needle stick induced stress) on measured hormonal levels, a 10-minute habituation period and another 10-minute baseline rest will be used before a 5.0-mL venous blood sample is obtained to measure baseline oxytocin and prolactin. The mother will then feed her infant as usual, e.g., breastfeeding, formula feeding, or mixed. Based on previous studies with 6 or 7 repeated hormonal measures around a feeding episode, we expect the typical peaks to occur at about 3 minutes for oxytocin and 30 minutes for prolactin after the onset of breastfeeding or pumping. Thus we will obtain 5.0-mL blood samples repeatedly at 3 and 30 minutes after the onset of feeding or pumping. Plasma oxytocin and prolactin will be assayed at [name] lab in UNC at Chapel Hill (see **Letter of Support**). The level of oxytocin will be measured by enzyme immunoassay with extraction (Enzo Life Sciences). The level of detection for oxytocin is 1.1 pg/mL and intra-assay and inter-assay coefficient of variation (CV) are 4.6% and 8.7%, respectively. Prolactin will be measured with commercial radioimmunoassay (MP Biomedicals) with level of detection being 1.0 ng/mL and intra-assay and inter-assay CV being 5% and 9%, respectively.

**Comments.** We recognize the timings for peak oxytocin and prolactin vary among individuals. Using the average peak times (3 and 30 minutes, respectively) is a cost-efficient way to capture hormonal responses.

*Mother-infant bonding.* Mother-infant bonding will be measured with the Postpartum Bonding Questionnaire (PBQ) at all postpartum visits. PBQ is a 25-item scale reflecting a mother's feelings or attitudes towards her baby, such as "I feel close to my baby" and "I regret having this baby". Cronbach's alpha was 0.76 for the total PBQ scale, and test-retest reliability was 0.95, 0.95, 0.93, and 0.77 for the 4 subscales (impaired bonding, rejection and anger, anxiety about care, and risk of abuse), respectively. PBQ is a valid screening tool for bonding disorders and is well correlated with Kennerley Blues Scale.

*Mother-infant interaction.* At 1, 3, and 5 months postpartum, maternal and infant behaviors will be assessed during observations of mother-infant interactions during free play in the PI's lab. The observation room will be set up with toys on top of a colorful blanket placed on the floor. Mothers will be asked to spend some time with their infants as they normally would at home. These interactions will be videotaped for 10 minutes and independently coded by two coders blinded to group assignment or other information about mothers and infants. These observations will be coded using 5-point rating scales originally developed by Clark and used extensively in our prior studies led by [name] (Co-I). Three composite maternal scales will be derived: maternal sensitivity, negative affect, and positive engagement. Three composite infant behavior scales will be computed: infant responsiveness, positive affect, and negative affect. These scales are reliable and valid across different samples of substance using women, including pregnant smokers.

*Maternal stress.* We will measure maternal stress with Perceived Stress Scale (PSS) at enrollment and all postpartum visits. The 14-item PSS measures subjective stress or the degree to which life situations are appraised as stressful. Participants will report how often they have felt upset, nervous, angered, in control, or that they have coped effectively in the past month. Cronbach's alpha of PSS was 0.85 and test-retest reliability was 0.85. It was correlated with life-events, depressive and physical symptomatology, and social anxiety.

*Maternal negative affect.* Maternal negative affect will be measured at enrollment and all postpartum visits using the Positive and Negative Affect Schedule (PANAS). The 10 items on negative affect include being distressed, upset, guilty, ashamed, hostile, irritable, nervous, jittery, scared, and afraid. Participants will rate their experience of each particular emotion in the past few weeks. With this time frame, its Cronbach's alpha was 0.87 and test-retest reliability was 0.48. In addition, we will measure maternal anxiety with the State-Trait Anxiety Inventory and postpartum depression with the Edinburgh Postnatal Depression Scale.

**3.1.10 Covariates.** We consider partner smoking, maternal secondhand smoke exposure, education, household income, health motivation, perceived social support, as covariates. They may confound our results and will be controlled in data analysis if not comparable between intervention and control groups.

**3.1.11 Economic costs.** We will collect information on intervention (not research and development) costs such as personnel, recruitment, materials, compensation, incentives, and transportation. We will include outcome costs for formula, medical care of NICU stay and sick child visits, and parental absenteeism for infant illness.

**3.1.12 Statistical Analysis.** *Specific Aim 1 (Breastfeeding promotion and postpartum smoking relapse).* The timing of postpartum smoking relapse (outcome) will be analyzed with Cox regression model by including group assignment (intervention vs control), smoking status (1=smoking, 0=non-smoking), the observed time, and significant covariates. The proportional hazard ratio of postpartum smoking relapse between two groups will be calculated. We will estimate Kaplan-Meier survival curves to visually compare smoking trajectories. Intent-to-treat analysis will be used with all randomized participants being included in their originally assigned groups. Dropouts, losses to follow-up, fetal deaths, and miscarriages will be coded as missing data on smoking status. If missing data on smoking status is more than 20%, we will run pattern mixture models and sensitivity analyses. A supplemental analysis will be run to examine *prenatal* smoking relapse during pregnancy.

*Specific Aim 2 (Mediation analyses on mechanisms).* We will use dynamic path analysis to examine the mechanisms through which breastfeeding reduces smoking relapse. The dynamic path analysis includes simultaneous fitting of the Aalen additive hazards model (the R package 'timereg') and ordinary path analysis (PROC TCALIS in SAS). It fits our survival data with internal time-dependent mediators (e.g., oxytocin or prolactin) and a counting process as the outcome (i.e., smoking relapse). Hormonal baseline level and response to infant feeding (oxytocin or prolactin) will be included into the model as independent mediators. We will estimate the direct, indirect (through one or multiple mediators), and total effects of breastfeeding on smoking relapse (**Figure 1**). The PI has sufficient experience in mediation analysis.

**3.1.13 Sample size.** According to the literature, we estimate 45% rate of smoking relapse by 6 months postpartum in the control group. Assuming 45% protection effect of breastfeeding against postpartum smoking relapse, we estimate 25% (45%\*[1-45%]) rate of smoking relapse by 6 months postpartum in the intervention group. The corresponding sample size is 98 per group with type 1 error  $\alpha$  of 0.05 and power  $1-\beta$  of 0.8 to detect significant difference in smoking relapse between two groups in the larger R01 project. If 9-month postpartum smoking relapse rates (70% control vs 39% intervention) are used, the corresponding sample size is 46 per group. Therefore, 30 participants per group for this pilot study should provide sufficient sample size to test feasibility and efficacy as well as provide preliminary data regarding mediators and cost-effectiveness.

**3.2 Potential Problems & Alternative Strategies.** A potential challenge for the proposed project is to recruit a sufficient number of pregnant ex-smokers. If significant delay is observed, we will expand recruitment areas, use direct mailing, and advertise in local media. Another potential problem is attrition during intervention and follow-up periods. We expect 20% attrition rate due to dropouts, losses to follow-up, miscarriages, and fetal deaths. If we lose contact, we will reach out to the 3 people that have close relationship with the participant indicated at enrollment. We will recruit more participants to ensure sufficient statistical power if attrition is high.

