**3.1.3 Screening.** Interested participants will sign consent forms and complete a survey on socio-demographics, pregnancy, medical history, mental health, history and status of cigarette smoking, use of other tobacco or nicotine products, alcohol and other substance use, and infant feeding plan. Those who had quit smoking cigarettes within 3 months before or during this pregnancy will be invited for lab screening to verify their current non-smoking status by urine cotinine (metabolite of nicotine). Collateral reports (e.g., from employer, partner, friend, or relative) or medical records will be used to verify their previous smoking history. Eligible participants

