**Figure 1. Conceptual Model for Breastfeeding and Smoking Abstinence\***

\* Other hormonal mechanisms, such as progesterone, estrogen, ACTH, cortisol, and tetraiodothyronine (T4), will be included in the larger R01 grant.

must be at 28 weeks of pregnancy or earlier to ensure adequate time for prenatal breastfeeding intervention. Exclusion criteria are teen pregnancy (<18 y); current use of other tobacco or nicotine products; medical conditions contraindicating breastfeeding such as HIV infection, active tuberculosis, and breast removal; current heavy drinking (more than 2 drinks a day); current use of other psychoactive substances; being strongly against breastfeeding; and non-English speakers. To increase the possibility to obtain a representative sample of the generable population, the study will be advertised as a program to promote healthy infant feeding among pregnant women without requiring breastfeeding intention or mentioning smoking relapse prevention. We will not exclude women without current intention to breastfeed (28.6% in our pilot survey), unless they are strongly against breastfeeding (4.8%). Similarly, we will not exclude women who plan to relapse after delivery (0% in our pilot survey), as our breastfeeding promotion may motivate them to maintain abstinent for a longer period especially if they know tobacco metabolites are concentrated in breast milk.

**3.1.4 Pre-test visit.** During this visit, we will measure the participant's urine cotinine, height, and body weight. Participants will complete a survey on smoking temptations, nicotine dependence before quitting, smoking cessation history, self-efficacy to maintain smoking abstinence, smoking environment including partner smoking behaviors, breast health, breastfeeding knowledge, breastfeeding history, relationship with partner and other family members, social network, stress, negative affect, physical activity, sleep, and diet.

**3.1.5 Randomization.** At 28 weeks of pregnancy, eligible participants will be randomized into either the intervention group (N=30) or the control group (N=30) using a sequence of random numbers in blocks of 2, which can ensure equal or close numbers of participants between the two groups throughout the project.

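### Cotinine of 50 ng/mL defines current smoking, but no recording of other nicotine use is described after entry, and no rule covers a positive test with a zero-cigarette calendar

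*Combined protocol and SAP*

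**What the plan says.** Section 3.1.8 (Timing of maternal postpartum smoking relapse) uses two sources.

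- **Self-report.** "The participant will use a calendar to record the daily number of cigarettes smoked, if any, throughout the study period". The relapse date is the first postpartum day of a pattern in which the woman "has smoked for 7 consecutive days, or has smoked at least once each week over 2 consecutive weeks".
- **Assay.** "The self-reported smoking abstinence will be biochemically confirmed by urine cotinine tests with HPLC-MS/MS assay", and "a cut-off point of 50 ng/mL urine cotinine will be used to define current smoking".

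Other nicotine sources appear only at entry. The screening survey in section 3.1.3 covers "use of other tobacco or nicotine products, alcohol and other substance use, and infant feeding plan", and the exclusion criteria in the same section include "current use of other tobacco or nicotine products". Section 3.1.3 also glosses urine cotinine as a metabolite of nicotine.

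After entry, Table 1 has one relevant row, smoking status, at every postpartum visit. The covariates in section 3.1.10 include partner smoking and secondhand smoke but no other nicotine product. The Cox model in section 3.1.12 takes smoking status coded 1 or 0, without saying which source sets the code.

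**The concern.** The plan treats other nicotine products as relevant at screening. It then relies on a nicotine marker until 9 months postpartum, roughly a year after randomisation at 28 weeks, without describing any further question about those products.

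Two different women produce the same record: a zero-cigarette calendar and cotinine at or above 50 ng/mL. One has stayed off cigarettes with nicotine replacement or an e-cigarette. The other has returned to tobacco in a form that the calendar does not count. Neither is concealing cigarettes; her calendar and her assay are both accurate. Only a record of product use could tell the two apart, and if it is not collected at the time it may not be recoverable.

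If such women are coded as relapsed, the primary outcome mixes cigarette relapse with nicotine switching. Only cigarette-abstinent women can be misclassified in this way. If the intervention works, its arm holds more of them, so even equal product use in the two arms dilutes the contrast. The pilot is meant to provide preliminary data for the larger R01 trial, so a diluted estimate would carry forward into that design.

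**Working it through.** **Inputs.** Section 3.1.13 gives 9-month relapse of 70% (control) and 39% (intervention), 6-month relapse of 45% and 25%, α = 0.05, power 0.80 and 30 women per group. The documents give no rate of switching to other nicotine products. The share *s* below is my assumption, shown from 2% to 20%.

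**The plan's own figures first.** Take the pooled-variance formula for two proportions, two-sided, with d the difference between the two rates: n′ = [1.96·√(2p̄q̄) + 0.8416·√(p₁q₁ + p₂q₂)]² / d². Then apply the continuity correction n = (n′/4)·[1 + √(1 + 4/(n′d))]².

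- 9 months: n′ = 39.3, n = 45.5, rounded up to 46.
- 6 months: n′ = 88.1, n = 97.8, rounded up to 98.

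Both match section 3.1.13 and are not in dispute.

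**Effect of switching.** Suppose a share *s* of cigarette-abstinent women use another nicotine product, all of them test at or above 50 ng/mL, and all are coded as relapsed. Then observed relapse = p + s(1 − p). With equal *s* in both arms the difference becomes (1 − s) × 31 points. The number of women affected per arm of 30 is 30·s·(1 − p).

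| s, both arms | Control | Intervention | Difference (points) | RR | Women affected, control / intervention |
|---|---|---|---|---|---|
| 0 | 70.0% | 39.0% | 31.0 | 0.56 | 0 / 0 |
| 2% | 70.6% | 40.2% | 30.4 | 0.57 | 0.2 / 0.4 |
| 5% | 71.5% | 42.0% | 29.5 | 0.59 | 0.5 / 0.9 |
| 10% | 73.0% | 45.1% | 27.9 | 0.62 | 0.9 / 1.8 |
| 20% | 76.0% | 51.2% | 24.8 | 0.67 | 1.8 / 3.7 |

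Worked line for 10%: control 0.70 + 0.10 × 0.30 = 0.730; intervention 0.39 + 0.10 × 0.61 = 0.451; 0.451 / 0.730 = 0.62.

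**Sample size on the diluted rates**, same formula with continuity correction:

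- 9 months: 46 per group becomes 48 (2%), 50 (5%), 55 (10%) and 66 (20%).
- 6 months: 98 per group becomes 104, 112, 128 and 165.

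**Unequal shares, 9 months.**

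- 5% control, 15% intervention: 0.70 + 0.05 × 0.30 = 0.715 and 0.39 + 0.15 × 0.61 = 0.4815. The difference is about 23 points, RR 0.67.
- 15% control, 5% intervention: 0.70 + 0.15 × 0.30 = 0.745 and 0.39 + 0.05 × 0.61 = 0.4205. The difference is about 32.5 points, above the planned 31, while RR is 0.56, essentially as planned.
- 10% control, 0% intervention: 0.730 and 0.390. The difference is 34 points, RR 0.53, an exaggeration on both scales.

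These are cumulative proportions at 9 months. They do not model event dates in the Cox analysis, because the plan gives no rule for dating such events.

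**The case against.** The strongest objection is that the step from a positive cotinine to a primary-outcome event is an inference. The relapse date rests on a smoking pattern. Cotinine is given the roles of confirming reported abstinence and defining current smoking at a cut-off. A reader might infer that the plan counts every product switcher as relapsed in the Cox model. The documents do not support that: they never say what happens when the assay is positive and the calendar shows zero, or what date would apply. This stands, and it limits the finding to classification at a visit plus a missing rule.

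A reader might also infer that other nicotine use is definitely never recorded after entry. That is too strong as well. The content of the postpartum smoking-status assessment is not shown, so one can say only that no such recording is described.

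The size may be small. Women enter free of other nicotine products, with cotinine checked at screening and measured again at the pre-test visit, so *s* counts only new use. Section 3.1.6 states that the trial has no component aimed directly at smoking relapse. At 2% to 5% the relative risk moves only from 0.56 to 0.57 or 0.59. In a pilot of 60, even 10% means about one control and two intervention women. This stands too, which is why the low end of the range is shown.

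Finally, whether a return to nicotine in another form counts as relapse is an endpoint choice. The plan's interest in tobacco metabolites in breast milk could support the wider definition. The documents do not establish that a cigarettes-only endpoint is the right one.

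None of this answers the central gap: whichever endpoint is chosen, the plan describes no data from which the two kinds of women could be told apart.

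**Conclusion.** The point holds as a measurement gap, with medium confidence. As written, a cigarette-abstinent woman using another nicotine product can meet the definition of current smoking at a visit. No later recording of such use is described, and no rule classifies or dates the discordant result. Contamination of the primary outcome is probable but not specified.

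The size is illustrative. It rests on an assumed switching share, on every switcher reaching the cut-off at a tested visit, and on each being coded as relapsed. With equal shares, the relative risk at 9 months moves modestly below 5% and noticeably at 10% to 20%. With unequal shares the direction is open, and nothing in the documents says which arm would switch more. A reader should not conclude that the trial's result will be materially biased. This is a cheap improvement that has to be made before data collection.

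**What to change.** In section 3.1.8:

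1. Add a column to the existing daily calendar, and one item at each postpartum visit, for any other tobacco, e-cigarette or nicotine-replacement use.
2. State before analysis whether the primary endpoint is cigarette relapse or any nicotine or tobacco use. The choice is the sponsor's.
3. State how cotinine of 50 ng/mL or more with a zero-cigarette calendar is classified and dated, with and without declared product use.
4. Report the definition not chosen as a sensitivity analysis.

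The cost is one column, one question per visit, a short rule and one extra analysis, with no new assay, visit or staff. If the cigarette definition is primary, there is a small downside: cotinine cannot verify abstinence at visits with declared product use, so those visits rest on self-report. The any-nicotine analysis bounds this.

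### Hormone draws are timed from the onset of feeding or pumping, but the expected peaks from the onset of breastfeeding or pumping, so a bottle-first mixed feed can miss the oxytocin rise

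*Combined protocol and SAP*

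**What the plan says.** All of the sampling text is in section 3.1.9 (Mediator measures, maternal plasma oxytocin and prolactin) of the combined protocol and SAP.

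- **Stimulus.** Hormone release is described as "often pulsatile and stimulated by suckling or pumping".
- **Expected peaks.** From studies with 6 or 7 measures around a feed, "we expect the typical peaks to occur at about 3 minutes for oxytocin" and at about 30 minutes for prolactin. Both times are counted "after the onset of breastfeeding or pumping".
- **Sampling rule.** The next sentence draws the conclusion: "Thus we will obtain 5.0-mL blood samples repeatedly at 3 and 30 minutes after the onset of feeding or pumping".
- **What happens in the session.** "The mother will then feed her infant as usual, e.g., breastfeeding, formula feeding, or mixed". Sessions take place at 1, 3 and 5 months postpartum.
- **Derived variable.** "The hormonal response to feeding will be calculated as the difference between the baseline and the peak during feeding".

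The comment that closes this part of section 3.1.9 accepts that peak times differ between women and defends the two average times as cost-efficient. It does not discuss what starts the clock. Under Specific Aim 2 in section 3.1.12, the baseline level and the response to feeding enter the dynamic path analysis as separate mediators.

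**The concern.** The rule for the draws is presented as following from the peak times, but the two sentences count from different events. They agree only if the feed begins at the breast or with the pump. Section 3.1.9 allows feeds that do not, because a mixed feed is permitted and its order is left to the mother.

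In a bottle-first mixed feed the clock would start while nothing is yet stimulating release. The design has one draw aimed at each hormone's peak, so no second reading near the oxytocin peak could recover it. The recorded response would then be too small because of when the blood was taken.

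This error would not be random scatter around the peak, because it arises only in one feeding mode. Understated oxytocin responses in bottle-first mixed feeders would make them look more like formula feeders. That would dilute a contrast of any breastfeeding against none, and exaggerate a contrast of exclusive against mixed feeding. Preliminary mediator data are a stated purpose of the pilot (section 3.1.13). If onset times are not recorded, no later analysis can correct the timing.

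**Working it through.** The plan states no figure that depends on the time anchor, so there is nothing to reproduce. The check compares the anchors and then does the timing arithmetic.

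**Step 1. Anchors by type of session.** The peaks run from breastfeeding or pumping; the draws run from feeding or pumping.

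| Session | Event that starts the clock, read literally | Start of stimulus | Agreement |
|---|---|---|---|
| Breast only | First latch | First latch | Yes |
| Pump, then feed that milk | Pump start | Pump start | Yes |
| Mixed, breast first | First latch | First latch | Yes |
| Mixed, bottle first | First bottle | First latch, later | No |
| Formula only | First bottle | None | Not applicable; a feeding anchor is needed |

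**Step 2. Is the order fixed elsewhere?** Component #5 in section 3.1.6 tells mothers to breastfeed first, but only for the optional early limited formula given to at-risk infants. It does not govern the sessions at 1, 3 and 5 months. For pumping, section 3.1.8 describes one order: "For a mother who pumps milk, staff will observe pumping combined with the resulting milk being fed to the infant". That is pump first, and it is written for verifying breastfeeding status. No section says which onset counts in a mixed feed, or that the times of latch, pump or bottle are recorded.

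**Step 3. Timing.** Let L be the minutes from first bottle to first latch. L is an assumption; the documents give no value.

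Time since suckling began = 3 − L at the oxytocin draw and 30 − L at the prolactin draw.

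| L (min, assumed) | Oxytocin draw (min after latch) | Prolactin draw (min after latch) |
|---|---|---|
| 0 | 3 | 30 |
| 2 | 1 | 28 |
| 3 | 0 | 27 |
| 5 | −2 | 25 |
| 10 | −7 | 20 |
| 15 | −12 | 15 |
| 20 | −17 | 10 |

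At L = 3 or more, the oxytocin draw is at or before the start of suckling. The prolactin draw stays after it for any L below 30.

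**Step 4. Effect on a group mean.** Suppose a share f of lactating mothers is sampled this way, their measured oxytocin response is zero, and their true mean response equals that of the others. The measured mean is then (1 − f) times the true mean: 0.95 at f = 5%, 0.80 at f = 20% and 0.50 at f = 50%. The share f is also an assumption, so these figures only illustrate the scale. The sessions at risk are some unknown part of at most 60 × 3 = 180.

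**The case against.** The strongest reply is that the plan measures the response to a usual feed, not to suckling. On that reading, a small rise in a bottle-only session is a true value, and a general feeding anchor is unavoidable for mothers with no latch or pump time. This stands for bottle-only sessions, and the fix respects it. It does not rescue the bottle-first mixed feed: the response is defined with the peak during feeding, and a draw taken before suckling cannot be that peak when suckling follows.

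A second reply is that fixed draw times are an admitted approximation and that the session is observed by study staff. The admission concerns variation between women in time to peak, not a clock that starts before the stimulus. Observation helps only if staff are told which onset to use and to write it down.

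Three stronger readings are tempting, and the documents do not support them.

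- **That pumping mothers are mistimed.** Pumping onset is named in both sentences, and the only order described is pumping before feeding. What remains is an unspecified case, a bottle given before pumping, which the documents do not describe.
- **That affected mothers will be recorded as non-responders on both hormones.** This needs bottle-first order and a lead of about 3 minutes or more, neither of which is documented. It concerns oxytocin; prolactin would be read early.
- **That mixed feeding is known to be common.** The pilot survey in section 1 reports 22.2% exclusive breastfeeding in the first week, among 18 postpartum women. The other 77.8% is not split into mixed and formula-only, and the week is not one of the session times. The survey women also did not receive this intervention.

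**Conclusion.** The point holds in a limited form. Section 3.1.9 counts the peaks from one event and the draws from a broader one. Read literally, the rule takes the only peak-timed oxytocin sample at or before the stimulus in any mixed feed where the bottle leads by 3 minutes or more, and samples prolactin L minutes early. No other section resolves this.

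The size is unknown, because both the lead time and the share of bottle-first feeders must be assumed. The effect is confined to the hormone-response mediator in the exploratory Aim 2 analysis. A reader might infer that the smoking-relapse result or the sample size is at risk; neither uses these samples. The change is still worth making before the first session, because it needs no extra blood and mistimed samples cannot be repaired afterwards.

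**What to change.** In section 3.1.9, replace the single anchor with a rule by session:

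- If any suckling or pumping takes place, start the 3- and 30-minute clock at first latch or pump start, whichever comes first. Otherwise start it at the first bottle.
- Ask the mother before the feed how she intends to proceed, so that staff know which anchor applies. Do not change how she feeds.
- Record the clock times of latch, pump, bottle and each draw. If a session departs from what was intended, the actual lag is then known.
- Carry session mode (suckling, pumping, mixed with its order, bottle only) into the Aim 2 data set.
- Keep the response values from bottle-only sessions, including those of lactating mothers, and flag them by mode. Dropping them would create missing data that depend on feeding mode, which is the exposure under study.

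The cost is a short change to the session procedure and one timing form, with no additional samples. Sessions with a bottle-first mixed feed run longer by about the bottle lead time, and the gap between the baseline draw and the stimulus grows by the same amount.
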